At the final stage, hypotheses will be tested using Mixed Effects models, a generalized linear model described by Gibbons et al.⁹¹, Hedeker et al.⁹² and Laird et al.⁹³. Responses at baseline, throughout treatment (sessions 7, 13, 21), post treatment (session 26), 3- and 6-month follow-up will be nested within subjects. Intercept and slope will be modeled as random effects nested within subject; Treatment group, time, and group-by-time interaction will be a fixed effect. A fully saturated treatment by time model will be utilized for inference. Co-variance structure will be chosen based on Akaike's Information Criterion (AIC). Data will be analyzed from all randomized subjects on whom we have a baseline assessment and at least one post-baseline evaluation. If it is needed based on analyses on stage one, baseline covariates (e.g., demographics) will also be added to the model. All hypothesis tests will be intent-to-treat, and will be two-sided at the .05 level. We will adjust p-values for multiple testing within each hypothesis separately by using a Bonferroni correction whenever more than one variable is being tested. Although we didn't have any drop-out in out pilot study, we included a drop-out rate of 10% after the baseline assessment but prior to the first post-baseline evaluation in our power analyses.

Hypothesis 1.1-1.3: Relative to those assigned to ET alone, CREST participants will show significant reduction in **hoarding severity** (primary outcome), improvement in **functioning** (both functional capacity and self-reported functioning; secondary outcomes) and improvement in **quality of life** over time.

- Independent Variables: Treatment Groups (CREST and ET), Time points (baseline, throughout treatment (sessions 7, 13, 21), post-treatment (session 26), 3 and 6-month follow-up).
- Dependent Variable: Hoarding severity (SI-R), Functioning (UPSA, USORT, SLOF, WHODAS 2.0.), Quality of Life (Neuro-QOL).

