Power analyses are performed for all hypotheses, incorporating the longitudinal nature of the design. Within this design, repeated observations within subjects are potentially correlated. This has a profound impact on the resulting tests of significance⁹⁸. When the within subject correlation is properly incorporated, the repeated measures analysis takes full advantage of all information obtained from each subject, thereby greatly increasing statistical power over methods that compare treatments cross sectionally⁹⁹. Using the method described by Diggle, Liang, & Zeger¹⁰⁰ and Ahn et al.¹⁰¹, power calculations can be made for repeated measures designs under specified assumptions. Hedeker, Gibbons, & Waternaux¹⁰² extend Diggle et al.¹⁻³'s method for various covariance structures. Procedures describes by Hedeker et al.¹⁰² for Random Regression Models which incorporated these principles was used for the proposed study to estimated needed sample size (RMASS program provided by Hedeker for the Random Regression Model). The design assumptions consist of a 2 treatment groups and up to 7 visits (baseline, sessions 7, 13, 21, 26, and 3- and 6-month follow-up) where the slope is the dependent measure. Other assumptions used were alpha-level, nature of the hypothesis (two-sided versus one-sided), drop-out rate, and variance-covariance matrix of the longitudinal data. We assume a Type-I error level (alpha-level) of .01 to 0.05, drop-out rate of 15% and an autoregressive covariance structure. Data reported in the preliminary studies section which included our own pilot studies were used to calculate effect sizes. From the preliminary analysis of pilot study, the estimated standard deviation (SD) for SI-R score ranges from 12.75-12.82 and the between visit correlation coefficient of 0.71. We considered a range of estimates of stand deviations of 12.5, 12.8 and 13.0, and correlations of .45 to 0.70 in our power analysis. We have reported large effect sizes of 1.02 and 1.51 from our previous studies which converted to differences of 60 to 37 for our primary outcome. However, for these calculations, we conservatively selected smallest clinically meaningful differences that we would like to be able to detect. This was then converted to a medium effect size, defined mathematically as a between-group difference increasing linearly from 0 at baseline to .5 SD units at the last time point. Calculations using the above assumptions indicated that the study will have minimum power of 80% to yield a statistically significant result for a medium effect size with the proposed sample size of 136 patients (68 for each of the two groups).

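### The minimum power of 80% claimed for 136 patients does not follow from the stated inputs under the analysis model in the Statistical Plan

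*Combined protocol and SAP*

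**What the plan says.** The Power Analysis section bases the sample size on the slope over up to seven visits. The group difference grows linearly from 0 at baseline to 0.5 SD at the last visit. Correlations run from .45 to .70 (the pilot between-visit value was 0.71). It adds: "We assume a Type-I error level (alpha-level) of .01 to 0.05, drop-out rate of 15% and an autoregressive covariance structure". From these it concludes that "the study will have minimum power of 80% to yield a statistically significant result for a medium effect size" with 68 patients per group.

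The Statistical Plan describes the analysis differently:

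- Fixed effects: "Treatment group, time, and group-by-time interaction will be a fixed effect".
- Random effects: "Intercept and slope will be modeled as random effects nested within subject", with the covariance structure selected by AIC.
- Inference: "A fully saturated treatment by time model will be utilized for inference".
- Error level: "All hypothesis tests will be intent-to-treat, and will be two-sided at the .05 level".
- Drop-out: "we included a drop-out rate of 10% after the baseline assessment but prior to the first post-baseline evaluation in our power analyses".

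**The concern.** The power statement is the only justification given for 136 patients, and it appears to describe a different model from the one that will be fitted. Four things that drive power are unstated or stated differently in the two sections: the term tested (linear slope or a contrast from a saturated model), whether the baseline difference is estimated or fixed at zero, the covariance, and the drop-out rate. The Power Analysis also does not say which pair of visits its correlation refers to.

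If the choices matter little, this is only a reporting gap. If they matter a lot, a reader cannot tell how likely the primary SI-R test is to detect 0.5 SD, and a null result would be hard to interpret.

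**Working it through.** **Inputs.** From the Power Analysis: 68 per arm; seven visits; difference 0 to 0.5 SD; autoregressive covariance; r from .45 to .70; 15% drop-out. From the Statistical Plan: two-sided .05. In SD units the SI-R standard deviation cancels.

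**Assumptions.** Visits are equally spaced. The lost 15% contribute nothing, so n = 68 × 0.85 = 57.8 per arm. The correlation r is either between adjacent visits, or between baseline and last visit (adjacent correlation r^(1/6)).

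**Method.** With t = j/6 for j = 0 to 6, the vector of group differences has mean 0.5t and variance 2Σ/n. For generalised least squares (GLS), power = Φ(0.5/SE − 1.960), with SE² = 2/(n × I):

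- baseline difference fixed at zero: I = t′Σ⁻¹t
- baseline difference estimated: I = t′Σ⁻¹t − (1′Σ⁻¹t)²/(1′Σ⁻¹1)

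**Reproducing the printed figure** (adjacent r = .70, zero baseline):

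- t′Σ⁻¹t = Σ(0.3j + 0.7)²/(36 × 0.51), j = 1 to 6, = 19.95/18.36 = 1.0866.
- n for 80% power = 2 × (1.960 + 0.842)²/(0.25 × 1.0866) = 57.79.
- 57.79/0.85 = 67.98 per arm, the plan's 68.
- Over r = .45 to .70, power is 80.0–88.1%, with the minimum at r = .70.

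**The same case with the group term kept:**

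- 1′Σ⁻¹t = 1.75/1.7 = 1.0294, and 1′Σ⁻¹1 = 1 + 6 × 0.3/1.7 = 2.0588.
- I = 1.0866 − 1.0294²/2.0588 = 0.5719.
- SE = √(2/(57.8 × 0.5719)) = 0.246.
- Power = Φ(0.5/0.246 − 1.960) = Φ(0.07) = 53%.

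**Power over r = .45 to .70, two-sided .05:**

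| Model | Adjacent-visit r | Baseline-to-last r |
|---|---|---|
| Group term kept, no loss | 57–60% | 79–96% |
| Group term kept, 15% lost | 50–53% | 73–94% |
| Group term kept, 15% leaving evenly | 54–57% | 76–95% |
| Random intercept and slope fit, no loss | 54–56% | 76–95% |
| Random intercept and slope fit, 15% lost | 47–49% | 69–92% |
| Zero baseline difference, 15% lost | 80–88% | 85–96% |

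In the second row, baseline-to-last r reaches 80% only from r = .54. If those lost keep their baseline score, the adjacent-visit entry becomes 53–56%.

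The random-effects rows apply the Statistical Plan's model to the same autoregressive data. With balanced data this is a test on individual least-squares slopes, with variance c′Σc and c = (j − 3)/28. A simulated slope test (40,000 runs, n = 58) gave 48.4, 47.1 and 49.1% at adjacent r = .45, .60 and .70.

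**Alpha .01**, the other end of the stated range. With 15% lost, the lowest power over r is 27% (adjacent, baseline estimated), 59% (adjacent, zero baseline), 50% (baseline-to-last, estimated) and 67% (baseline-to-last, zero). With zero baseline and no loss the minima are still 67.8% and 75.7%.

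**If the data truly follow a random intercept and slope** (group term kept, 15% lost, .05). With no slope variance (compound symmetry) power is 89–99%. It stays at 80% or more only while slope variance, as a fraction of baseline variance per visit squared, is at most (0.5/6)² × (57.8/2)/(1.960 + 0.842)² − (1 − r)/28. That is .006, .011 and .015 at r = .45, .60 and .70, or slope SDs of 1.0, 1.4 and 1.6 SI-R points per visit at SD 12.8. The documents give no slope variance.

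**Saturated model.** A last-visit difference has Φ(0.5/√(2/n) − 1.960) = 83% with no loss and 77% with 15% lost. At adjacent-visit r with 15% lost, the baseline-to-last change has about 48–53%, and the six-degree-of-freedom interaction about 26–28%.

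**The case against.** The strongest reply is that the printed figure reproduces. With the difference starting at 0, r read as adjacent-visit correlation and alpha .05, the minimum over the stated correlations is 80.0% at exactly 68 per arm. With the baseline difference fixed at zero the claim also holds under the other reading of r. Randomisation can justify that constraint. This stands: 136 is not an arithmetic slip. But a true baseline difference of zero is not the same as a model that imposes it, and the Statistical Plan lists treatment group among its fixed effects. That the original calculation omitted the group term is inferred from the match; the documents do not say so.

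A second reply is that alpha .01 may be meant for the five secondary measures after Bonferroni (.05/5), since SI-R is the single primary measure. This is plausible, and the .01 results should not be read as evidence against the SI-R test. They do show that the claimed minimum fails over the alpha range printed with it.

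A third is that a power calculation must assume some covariance, and AIC may select an autoregressive one. That is fair. But the random intercept and slope are stated without any slope variance, and the answer is sensitive to it.

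**Conclusion.** The claim of a minimum 80% power is wrong as written, because the stated inputs do not deliver it under the stated analysis model. With the group term kept, autoregressive data, two-sided .05 and 15% lost, slope power for 0.5 SD is 50–53% (adjacent-visit r) or 73–94% (baseline-to-last r). Under adjacent-visit r, the difference detectable with 80% power is 0.64–0.71 SD by GLS, from no loss to 15% lost. With the random intercept and slope fit it is 0.66–0.74 SD.

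The failure of the minimum is firm. The size of the shortfall is not: it depends on the meaning of r, the visit spacing, the timing of drop-out and the term tested, which are assumptions here. Under compound symmetry power exceeds 80%, so this does not show that the trial is underpowered. It shows that the plan cannot tell a reader whether the primary test has about 50% or over 90% power for a slope. Some saturated-model contrasts would have less.

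**What to change.** Re-run the power for the model and covariance in the Statistical Plan, and state in both sections:

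1. the term tested for SI-R: the linear group-by-time slope or one named contrast from the saturated model;
2. whether the baseline difference is estimated or fixed at zero;
3. which visits the correlation refers to and, for random effects, the slope variance assumed;
4. one alpha for SI-R, .05, as the Statistical Plan already has it;
5. one drop-out rate and pattern, reconciling 10% with 15%.

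Then replace the minimum of 80% with the resulting figure and its range. Under the autoregressive, adjacent-visit, estimated-baseline reading that would be about 50–60% for 0.5 SD by GLS, or 80% for about 0.64–0.71 SD.

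A linear-time model with a common baseline is an option, not a requirement. With adjacent-visit r and 15% lost it reaches 80% only for r up to .70, equal spacing and a difference growing linearly from baseline. At r = .70 it gives about 78% if visits are scaled in weeks (0, 7, 13, 21, 26, 39, 52, an assumption), and 77% if the difference is still zero at session 7.

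The cost is one recalculation, one or two sentences in the Statistical Plan and one paragraph in the Power Analysis. Restating needs no extra patients, though the printed power may be less favourable. Restoring 80% under the adjacent-visit reading by sample size alone would be a separate decision: about 130 to 136 per arm at the two ends of the r range if the lost 15% contribute nothing.
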